Appendix B: Exercise Handout and Calendar

- You will need a rolled-up towel for this exercise.
- Sit with your leg straight in front of you and placed the rolled-up towel behind the knee.
- Flex your thigh muscle to push your knee down on the towel without lifting your foot off the floor/bed.
- Hold this contraction for 3 seconds and then relax for 3 seconds.
- Repeat 10 times, or as instructed.

WEEK 1

MON	TUE	WED	THURS	FRI	SAT
 Quad exercise: 1 set of 10 reps  Walk: 10 min	 Quad exercise: 1 set of 10 reps	 Quad exercise: 1 set of 10 reps  Walk: 10 min	 Quad exercise: 1 set of 10 reps	 Quad exercise: 1 set of 10 reps  Walk: 10 min	REST

WEEK 2

MON	TUE	WED	THURS	FRI	SAT
 Quad exercise: 1 set of 10 reps  Walk: 10 min	 Quad exercise: 1 set of 10 reps	 Quad exercise: 1 set of 10 reps  Walk: 15 min	 Quad exercise: 1 set of 10 reps	 Quad exercise: 1 set of 10 reps  Walk: 15 min	REST

WEEK 3

MON	TUE	WED	THURS	FRI	SAT
 Quad exercise: 1 set of 10 reps  Walk: 15 min	 Quad exercise: 1 set of 10 reps	 Quad exercise: 1 set of 10 reps  Walk: 15 min	 Quad exercise: 1 set of 10 reps	 Quad exercise: 1 set of 10 reps  Walk: 15 min	REST

WEEK 4

MON	TUE	WED	THURS	FRI	SAT
 Quad exercise: 2 sets of 10 reps  Walk: 15 min	 Quad exercise: 2 sets of 10 reps	 Quad exercise: 2 sets of 10 reps  Walk: 15 min	 Quad exercise: 2 sets of 10 reps	 Quad exercise: 2 sets of 10 reps  Walk: 15 min	REST

WEEK 5

SUN	MON	TUE	WED	THURS	FRI	SAT
REST	 Quad exercise: 2 sets of 10 reps  Walk: 15 min	 Quad exercise: 2 sets of 10 reps	 Quad exercise: 2 sets of 10 reps  Walk: 15 min	 Quad exercise: 2 sets of 10 reps	 Quad exercise: 2 sets of 10 reps  Walk: 20 min	REST

WEEK 6

SUN	MON	TUE	WED	THURS	FRI	SAT
REST	 Quad exercise: 2 sets of 10 reps  Walk: 20 min	 Quad exercise: 2 sets of 10 reps	 Quad exercise: 2 sets of 10 reps  Walk: 20 min	 Quad exercise: 2 sets of 10 reps	 Quad exercise: 2 sets of 10 reps  Walk: 20 min	REST

WEEK 7

SUN	MON	TUE	WED	THURS	FRI	SAT
REST	 Quad exercise: 3 sets of 10 reps  Walk: 20 min	 Quad exercise: 3 sets of 10 reps	 Quad exercise: 3 sets of 10 reps  Walk: 20 min	 Quad exercise: 3 sets of 10 reps	 Quad exercise: 3 sets of 10 reps  Walk: 20 min	REST

WEEK 8

SUN	MON	TUE	WED	THURS	FRI	SAT
REST	 Quad exercise: 3 sets of 10 reps  Walk: 25 min	 Quad exercise: 3 sets of 10 reps	 Quad exercise: 3 sets of 10 reps  Walk: 25 min	 Quad exercise: 3 sets of 10 reps	 Quad exercise: 3 sets of 10 reps  Walk: 25 min	REST

WEEK 9

SUN	MON	TUE	WED	THURS	FRI	SAT
REST	 Quad exercise: 3 sets of 10 reps  Walk: 25 min	 Quad exercise: 3 sets of 10 reps	 Quad exercise: 3 sets of 10 reps  Walk: 25 min	 Quad exercise: 3 sets of 10 reps	 Quad exercise: 3 sets of 10 reps  Walk: 25 min	REST

WEEK 10

SUN	MON	TUE	WED	THURS	FRI	SAT
REST	 Quad exercise: 2 sets of 10 reps, 2x/day  Walk: 25 min	 Quad exercise: 2 sets of 10 reps, 2x/day	 Quad exercise: 2 sets of 10 reps, 2x/day  Walk: 30 min	 Quad exercise: 2 sets of 10 reps, 2x/day	 Quad exercise: 2 sets of 10 reps, 2x/day  Walk: 30 min	REST

WEEK 11

SUN	MON	TUE	WED	THURS	FRI	SAT
REST	 Quad exercise: 2 sets of 10 reps, 2x/day  Walk: 30 min	 Quad exercise: 2 sets of 10 reps, 2x/day	 Quad exercise: 2 sets of 10 reps, 2x/day  Walk: 30 min	 Quad exercise: 2 sets of 10 reps, 2x/day	 Quad exercise: 2 sets of 10 reps, 2x/day  Walk: 30 min	REST

WEEK 12

SUN	MON	TUE	WED	THURS	FRI	SAT
REST	 Quad exercise: 2 sets of 10 reps, 2x/day  Walk: 30 min	 Quad exercise: 2 sets of 10 reps, 2x/day	 Quad exercise: 2 sets of 10 reps, 2x/day  Walk: 30 min	 Quad exercise: 2 sets of 10 reps, 2x/day	 Quad exercise: 2 sets of 10 reps, 2x/day  Walk: 30 min	REST

Appendix C: Encouragement During 6-Minute Walk Test

After the first minute, tell the patient the following (in even tones): “You are doing well. You have 5 minutes to go.”

When the timer shows 4 minutes remaining, tell the patient the following: “Keep up the good work. You have 4 minutes to go.”

When the timer shows 3 minutes remaining, tell the patient the following: “You are doing well. You are halfway done.”

When the timer shows 2 minutes remaining, tell the patient the following: “Keep up the good work. You have only 2 minutes left.”

When the timer shows only 1 minute remaining, tell the patient: “You are doing well. You have only 1 minute to go.”

Do not use other words of encouragement (or body language to speed up).

Appendix D: Quadriceps Strength Testing

1. With the handheld dynamometer placed distally on the affected leg with the knee in 90 degrees flexion, participants will push against the dynamometer for 5 seconds.
2. Subjects will get two warm-up trials separated by a 1-minute rest period.
3. The first warm up will be 10 repetitions at 50% maximal effort, with contractions to be held for 5 seconds.
4. The second warm up will be 5 repetitions at 70% maximal effort, with contractions to be held for 5 seconds.
5. Subjects will then perform 3 repetitions of maximal effort, separated by two minutes of rest between each.
6. The test will be repeated on the other leg.

Appendix E: Western Ontario/McMaster Universities Osteoarthritic Index (Physical Function)

Think about the difficulty you had in doing the following daily physical activities due to your knee during the last 48 hours. By this, we mean your ability to move around and look after yourself.

Question: What degree of difficulty do you have?

	None	Mild	Moderate	Severe	Extreme
Descending stairs	└	└	└	└	└
Ascending stairs	└	└	└	└	└
Rising from sitting	└	└	└	└	└
Standing	└	└	└	└	└
Bending to the floor	└	└	└	└	└
Walking on flat surfaces	└	└	└	└	└
Getting in and out of a car, or on or off a bus	└	└	└	└	└
Going shopping	└	└	└	└	└
Putting on your socks or stockings	└	└	└	└	└
Rising from the bed	└	└	└	└	└
Taking off your socks or stockings	└	└	└	└	└
Lying in bed	└	└	└	└	└
Getting in or out of the bath	└	└	└	└	└
Sitting	└	└	└	└	└
Getting on or off the toilet	└	└	└	└	└
Performing heavy domestic duties	└	└	└	└	└
Performing light domestic duties	└	└	└	└	└

Appendix F: Western Ontario/McMaster Universities Osteoarthritis Index (Pain)

Think about the pain you felt in your knee during the last 48 hours.

Question: How much pain do you have?

	None	Mild	Moderate	Severe	Extreme
Walking on a flat surface	█	█	█	█	█
Going up and down stairs	█	█	█	█	█
At night while in bed, pain disturbs your sleep	█	█	█	█	█
Sitting or lying	█	█	█	█	█
Standing upright	█	█	█	█	█

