A sample size of 32 participants was calculated to be sufficient for a two-tailed significance level of 5% and a power of 80% (Appendix A). This was adjusted to 45 participants with knee osteoarthritis to allow for dropouts. Recruitment for this study will be conducted using a recruitment flyer and through the CIONIC website. Recruitment will be based on a first come

basis. Interested participants will complete a questionnaire to be reviewed according to the inclusion and exclusion criteria. Responses will then be reviewed, and prospective participants will be invited to schedule a virtual meeting with a study staff member who will screen the prospective subject for an understanding of the study and for their voluntary participation. All participants will be assigned a unique number using a computer random number generator and randomly assigned to a group by a researcher. All participants will receive their assigned intervention at their first lab visit.

Inclusion Criteria

- Persons with knee osteoarthritis between the ages of 22 and 75
- Ability to walk a duration of 30 minutes per walking session (with or without an assistive device), for three days per week
- Able to tolerate the device for up to 1 hour per lab session
- No recent change in medication or exacerbation of symptoms over the last 60 days
- Radiographic KOA K&L grade 2 or 3 or physician diagnosed mild or moderate KOA if radiographic imaging is not available
- No hyaluronic acid or cortisone injection into knees in previous 12 months

Exclusion Criteria

- Lower motor neuron disease or injury (e.g. peripheral neuropathy) that may impair response to stimulation
- Absent sensation in the impacted or more impacted leg

- Inadequate response to stimulation, as defined as inability to achieve muscle contraction or tolerate stimulation
- Inability to ambulate with the sleeve in place of an ankle foot orthosis (AFO)/knee ankle foot orthosis (KAFO) if utilized
- Use of FES devices in the past year
- Demand-type cardiac pacemaker or defibrillator
- Malignant tumor in the impacted or more impacted leg
- Existing thrombosis in the impacted or more impacted leg
- Fracture or dislocation in the impacted or more impacted leg that could be adversely affected by motion from stimulation
- History of knee surgery
- History of other types of arthritis
- History of neurological disease
- History of seizures or diagnosed with epilepsy/seizures
- Current pregnancy

Methodology

Overview of Study

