This study is a randomized controlled trial. Figure 2 depicts a flow diagram of the study design. Participants will be screened for eligibility through a questionnaire, and after study details are explained and consent is obtained, they will be invited to the study site. Assessments will be conducted at CIONIC Inc., and involve approximately 45 patients for a 12 week study period.

CIONIC

CIONC FOR ORTHOPEDICS

All subjects will be assigned an electrical stimulation system to wear on the most impacted leg and be prescribed a home-based exercise and walking program. Subjects will be randomly assigned into three groups: (a) control; (b) NMES+; (c) NMES+FES. The control group will not receive stimulation for the exercise and walking program, whereas subjects in NMES+ will receive stimulation during exercises, and subjects in the NMES+FES group will receive stimulation during exercises and walking. Outcome measures will be assessed at baseline, 6 weeks after baseline, and end of study (Table 2). Equipment and additional feedback will be collected at the end of study. These three groups will be analyzed using several outcome measures. Primary outcome measures of the study are quadriceps strength, perceived functional capacity, self-reported pain, and walking performance. Secondary interest will be adherence to program, thigh muscle volume, functional ability of the lower limb, and quality of life. The CIONIC system will be used to track adherence (duration of sessions, frequency of use).

[figure not shown]

Figure 2: Study flow

Table 2: Study overview

Comparison Groups	Treatment Schedule	Timing and Outcome Measures
Control (unstimulated exercise and walking)	Exercise: 5x/week for 12 weeks Progression every 3 weeks	At baseline, midpoint and end of study: Quadriceps strength Perceived functional capacity Self-reported pain Walking performance Thigh muscle volume Functional ability of lower limb Quality of life EMG activity
NMES+ (NMES+exercise and unstimulated walking)	Walking: 10 min, 3x/week for 12 weeks Progression up to 30 min by end of study	Weekly: Adherence to program
NMES+FES (NMES+exercise and FES+walking)		

Participant Identification, Recruitment & Informed Consent

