The study will be explained to the participants and written informed consent will be obtained before the initial lab visit. Physical measurements, performance tests, and questionnaire responses will be collected at three lab visits: initial, study midpoint (6 weeks), and end of study (12 weeks). Physical measurements will include height, weight, and thigh circumference of the impacted leg. If subjects report bilateral compromised legs, the most impacted/painful leg will be measured. Participants will be asked to complete four performance tests (maximal voluntary isometric contraction of the quadriceps, Five Times Sit to Stand Test (FTSST), 10-meter Walk Test (10mWT), and the 6-Minute Walk Test (6MWT)) and three questionnaires (Western Ontario/McMaster Universities Osteoarthritis Index physical function (WOMAC-PF) subscale, WOMAC-pain, and the Short Form-36). Order of the tasks at the lab visits are as follows: maximal voluntary isometric contraction of the quadriceps, FTSST, 10mWT, WOMAC-PF, 10mWT, WOMAC-pain, 6MWT, Short Form-36, and 6MWT. Instruction will be provided to the participants before beginning a new task, and the researchers will periodically gauge the subjects for a need for a break and understanding of the task. For the walking tests, subjects will be fitted with the electrical stimulation system to collect EMG/kinematic data, and depending on the subject's group assignment, stimulation may or may not be enabled. All subjects will be provided with and instructed to wear the electrical stimulation system for the subsequent 12 weeks. All subjects will be taught how to navigate the supporting app and receive a user manual on how to operate/care for the system. Subjects assigned to receive stimulation will be taught how to adjust parameters of the device using the supporting app. All participants will receive a handout explaining the exercise, and a calendar for the exercise and walking program (Appendix

B). Subjects will be informed to perform the exercise and walking program in an area free from obstacles. Lab visits may be up to 90 minutes in duration.

Exercise and Walking Program

The participants will wear the device during the 12-week exercise and walking program. This may range from 1 minute to 35 minutes per day (Appendix B).

Exercise Program

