Walking endurance (m) will be measured using the 6MWT using the same walkway utilized for the 10mWT. Participants will wear the Cionic Neural Sleeve during the two 6MWTs. For the 6MWT, the subject will be instructed to walk as far as possible for 6 minutes, up and down the pathway, and pivoting to turn at the end of each lap³¹. Timing will begin when the participant steps over the start line, and distance traveled will be recorded. Encouragement outlined in the guideline (Appendix C) will be given to the subjects after each minute, and participants will be instructed to stop at 6 minutes or prior, if they are unable to complete 6 minutes. Use of a walking aid and standing rests will be permitted. Normative values of people aged 40-80 years will be used as reference values³².

Secondary Measures

Adherence to Program

Adherence to the program will be measured by the usage log of the Cionic Neural Sleeve. The data collected from the Cionic Neural Sleeve worn on the affected limb/most affected limb will be recorded to monitor compliance to the program in number of repetitions and duration of walking.

Thigh Muscle Volume

Thigh muscle volume will be estimated using a measurement tape for thigh circumference and a prediction model. Thigh circumference (cm) will be measured from a point 15 cm proximal to the superior pole of the patella. The prediction model is as follows: Muscle volume (cm³)

=4226.3 – 42.5×age(year) – 955.7× gender(male=1, female=2) + 45.9×body weight(kg) + 60.0×thigh circumference(cm)³³. It was selected for this study for its correlation ($r^2 = 0.745$) to magnetic resonance imaging, the gold standard of measuring muscle volume³⁷.

Functional Ability of the Lower Limb

To measure functional ability of the lower limb, subjects will be asked to perform the FTSST. The FTSST requires participants to sit in a chair with their arms crossed over the chest and then to stand up/sit down for five times, as fast as possible³⁴. Subjects will be timed from the initial sitting position to the final standing position. Cut-off points of 10.8 and 12.8 seconds will be used as references for intermediate and poor function, respectively³⁵.

Quality of Life

The Short Form 36 (SF-36) is a generic measure of health status that measures self-reported functional health and well-being in the past four weeks in eight domains or two summary scores. Scores range from 0 to 100, with 0 representing extreme interference, and 100 representing no interference³⁶.

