Appendix A: Power Analysis

Power and Significance Level

[figure not shown]
These are set to standard,

Power = 0.8

Significance Level (alpha) = 0.05

Metric	Effect Size used in calculation	Required sample size when comparing participants' sessions (paired sample)	Required sample size when comparing group A to group B
WOMAC - Function bivariate	0.71 ²⁷	18	32
WOMAC - Pain bivariate	0.41 ²⁷	49	94
WOMAC - Function Standing/Walking bivariate	0.45 ²⁷	41	78

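### The WOMAC pain and function forms do not say which knee to score, although bilateral disease is allowed and only one leg is stimulated

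*Combined protocol and SAP*

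**What the plan says.** The Overview of Study gives the outcomes: "Primary outcome measures of the study are quadriceps strength, perceived functional capacity, self-reported pain, and walking performance". Perceived functional capacity is measured by WOMAC-PF and pain by WOMAC-Pain, at baseline, 6 weeks and end of study.

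- **The forms.** Appendix F begins "Think about the pain you felt in your knee during the last 48 hours". Appendix E begins "Think about the difficulty you had in doing the following daily physical activities due to your knee during the last 48 hours". Neither names a side, and the outcome definitions under Perceived Functional Capacity and Pain do not either.
- **The treated leg.** The Overview of Study states "All subjects will be assigned an electrical stimulation system to wear on the most impacted leg". This applies in all three groups; the control group wears the sleeve without stimulation. Adherence to Program likewise refers to a sleeve "worn on the affected limb/most affected limb".
- **Bilateral disease.** No inclusion criterion requires one-sided disease, and the exclusions are worded for either case, for example "Absent sensation in the impacted or more impacted leg". Lab Visits adds "If subjects report bilateral compromised legs, the most impacted/painful leg will be measured". That sentence directly follows the list of physical measurements (height, weight, thigh circumference). The questionnaires come after it, with no such rule.
- **Staff instruction.** Lab Visits also says that participants are instructed before each new task and that researchers check they understand it. It does not say that this instruction names a knee.

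**The concern.** The protocol recognises that a participant may have two affected knees and settles which leg counts for the physical measurement. It does not do so for the two self-reported primary outcomes. A participant with two painful knees could score the sleeved knee, the other knee, both together, or whichever is worse that day.

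Two consequences follow. First, an answer about a knee that stimulation does not reach carries less of the stimulation effect, so the difference between stimulation and control is pulled towards zero. Second, a participant who scores one knee at baseline and the other at 12 weeks adds noise to the change score, which also affects the planned before-and-after paired tests. The reference knee could even move because of treatment: if the sleeved knee improves enough, the other becomes the worse one.

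The forms do not record which knee was meant, so this cannot be recovered at analysis.

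**Working it through.** **Step 1: is there an instruction anywhere?** The places that could fix the scored knee are the outcome definitions, the Lab Visits text, Appendices E and F, and the statistical analysis section. None does. The one leg rule, in Lab Visits, belongs to the physical measurements. Strength is tested on both limbs, so it does not settle the matter for the questionnaires.

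**Step 2: reproduce the plan's figures.** Inputs from Appendix A: "Significance Level (alpha) = 0.05", power 0.8, effect size d = 0.71 for function and 0.41 for pain. The two-sided level is stated under Participation Selection and Randomization.

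n per group = 2 × ((1.960 + 0.842) / d)²

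- Function: 2 × (2.802 / 0.71)² = 31.1, rounded up to 32. The t-test solution is 32.13. Appendix A gives 32.
- Pain: 2 × (2.802 / 0.41)² = 93.4, rounded up to 94. The t-test solution is 94.35. Appendix A gives 94.
- Paired t-test: 17.59 and 48.65, rounded up to 18 and 49, as in Appendix A.

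So 32 and 94 are sizes per group, with no allowance for answers about another knee.

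**Step 3: a dilution model (assumption).** Suppose a share f of answers describes a knee on which stimulation has no effect, with the standard deviation unchanged. The standardized difference becomes d × (1 − f). The share is f = b × s, where b is the proportion with bilateral disease and s the proportion of those who score the unstimulated knee. The documents give neither. For scale, b = 50% and s = 50% gives f = 25%; f = 40% would need, for example, b = 80% and s = 50%.

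Diluted effect sizes for function: 0.71 × 0.95 = 0.67, 0.71 × 0.85 = 0.60, 0.71 × 0.75 = 0.53, 0.71 × 0.60 = 0.43. For pain: 0.41 × 0.95 = 0.39, 0.41 × 0.85 = 0.35, 0.41 × 0.75 = 0.31, 0.41 × 0.60 = 0.25.

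**Step 4: power.** Two-sample t-test, two-sided 5%. The 15 per arm is 45 / 3 before dropout, assuming equal allocation, since the ratio is not stated.

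| | f = 0 | 5% | 15% | 25% | 40% |
|---|---|---|---|---|---|
| Function, d = 0.71, 32 per arm | 80% | 76% | 66% | 55% | 39% |
| Function, d = 0.71, 15 per arm | 47% | 43% | 36% | 29% | 20% |
| Pain, d = 0.41, 15 per arm | 19% | 18% | 15% | 13% | 10% |

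The low values in the f = 0 column at 15 per arm come from the sample size, which is a separate issue. Only the fall along each row belongs to this point.

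**The case against.** Five arguments on the other side deserve weight.

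1. **The forms are not handed over in silence.** Staff give instruction before each task and check understanding. A reader might infer that the printed wording alone produces misdirected answers. The documents do not support that, because a verbal instruction could prevent it. But none is scripted, none is required to name a knee, and it could differ between visits. The risk is reduced, not closed.

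2. **Context favours the study knee.** The forms speak of one knee, the sleeve is on the worse leg, and the questionnaires are interleaved with walking tests done in the sleeve. This is inference, but it argues for a small f, which is why 5% is in the table. For the other knee to become the worse one also requires bilateral disease and a benefit large enough to reverse the order.

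3. **Bilateral disease is allowed, not predicted.** A reader might infer that it is expected in many participants. The Lab Visits sentence is conditional and no prevalence is given, so no value of f can be defended from the documents.

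4. **The dilution model may discount twice.** The effect sizes come from a cited study that cannot be checked here. If its scores already mixed both knees, 0.71 and 0.41 already contain some dilution. This stands, and it is a reason to treat the table as illustration.

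5. **Function belongs largely to the person.** Stairs, rising from sitting, and getting in and out of a car or bath depend on both legs, so naming one knee cannot isolate the treated side. This also stands: the point is clearer for pain.

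**Conclusion.** The point holds as an inexpensive improvement to the two forms. The text shows that bilateral disease is allowed, stimulation reaches one leg, and nothing fixes which knee is scored or keeps it the same over three visits. The consequence is possible attenuation of the comparison between stimulation and control, plus added noise. *Only one leg* applies to stimulation: walking uses both legs, and the exercise handout does not say which leg to exercise.

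The size is unknown. The table rests on an assumed f, no stimulation effect on the other knee, an unchanged standard deviation, and Appendix A effect sizes taken as undiluted. Under those assumptions the loss for function at 32 per arm runs from 4 percentage points at f = 5% to 41 at f = 40%. For pain at 15 per arm it runs from 1 to 9 points, from a base that is already low.

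A reader might go further and infer that the results would favour one arm or that false positives become more likely. Nothing in the documents shows either.

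**What to change.** - At the initial visit, before allocation, record the study leg (left or right) and whether disease is bilateral. Keep the study leg fixed for all visits.
- Print one line on Appendices E and F at all three visits: *Answer for the knee of the leg on which you wear the sleeve (left/right)*, with the side filled in. It works in every group because controls wear the sleeve too.
- Have staff read the same scripted sentence at each visit.
- Use the recorded bilateral status for a sensitivity analysis of both WOMAC outcomes.

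The cost is one printed line on two forms and two baseline fields. The change must be made before data are collected. The downside is slightly less comparability with published scores and with the protocol's improvement benchmarks of 14.48 (function) and 8.74 (pain). For function it isolates the treated knee only in part.
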